clinicians are promising candidates to deliver BBTI as they are specifically trained to deliver brief, solution-focused treatments to ensure efficient access to care. However, simply training PCMH clinician is rarely enough. This is especially true of evidence-based psychotherapies (EBPs) that often require accounting for patient-, provider, and systemic-level barriers in addition to substantial training to deliver care with fidelity. Implementation science has shown that an integrated set, or bundle, of interventions and strategies are needed to enhance the likelihood of successful uptake, adoption, and sustainable delivery of EBPs.

Implementation science also states it is critical to match known barriers to specific implementation strategies. Barriers to delivering behavioral insomnia treatment in Primary Care, informed by the PI's Career Development Award (CDA), were matched to Expert Recommendations for Implementing Change (ERIC) strategies to create a bundle of strategies. This study, a stepped-wedge, hybrid III implementation-effectiveness trial, will test the implementation strategy bundle (e.g., implementation blueprint, provider education, audit and feedback) in how well it improves and supports the uptake and sustainable delivery of BBTI in PCMH at four VAMCs (Baltimore, Durham, Minneapolis, and Philadelphia). The stepped-wedge is advantageous vs. a non-stepped trial as fewer sites are needed to achieve adequate power and all sites are exposed to the intervention in a sequential fashion. The hybrid design tests for level of *implementation* in real-world settings and Veteran-level treatment *effectiveness* of BBTI, both necessary for uptake, adoption, and sustainable delivery. Furthermore, taking a multi-method approach with implementation outcomes guided by the Reach, Effectiveness, Adoption, Implementation, and Maintenance (RE-AIM) framework, qualitative interviews, and surveys will provide valuable information about specific strategies that are effective given site-specific context.

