Aim 1. To compare the impact of training PCMH clinician to deliver BBTI (BBTI) vs. the impact of BBTI training plus 12-months of access to an implementation strategy bundle (BBTI+IS). Sites will be measured across three study phases: BBTI (pre-implementation), BBTI+IS (implementation), and maintenance (post-implementation). During the implementation phase, sites will have internal and external support from insomnia and implementation experts to enhance their implementation efforts. We hypothesize that BBTI+IS will result in more Veterans obtaining insomnia-related care in PCMH (R [primary outcome]), better treatment outcomes (E), greater uptake of BBTI by clinicians (A), improved treatment fidelity (I), and result in sustained BBTI delivery without implementation support (M). RE-AIM outcomes will allow for the evaluation and refinement of specific implementation strategies to use in future efforts to improve access to evidence-based insomnia care.

Aim 2. To identify specific strategies that help promote the implementation of BBTI in PCMH. Using qualitative interviews, we will evaluate site PI and PCMH clinician perspectives on BBTI training, and the impact of implementation strategies and barriers that continue to impede progress. Using surveys, completed by site PIs, we will identify specific strategies that help, or hinder, the implementation of BBTI in PCMH. Strategies identified as helping to implement BBTI in PCMH will help further adapt strategies to enhance implementation.

This proposal is responsive to VA ORD priorities of expanding access to Veterans for high quality clinical trials (e.g., a stepped-wedge, hybrid trial) and increasing the real-world impact of VA research. It also targets HSR&D research, and ORD clinical, priority areas of access to care, mental health, primary care practice, and virtual care and telehealth, within the framework of implementation science, a prioritized cross-cutting method.

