### **5.3 Informed Consent Procedures**

VA employee participants—site PIs and PCMH clinician—will be invited to participate in this trial (see section 5.4). Those who volunteer to participate will complete a verbal informed consent by phone, administered by study staff at the hub site in Pittsburgh. See Appendix 10.2 for the study information sheet that will be provided to all potential participants prior to consent. We are requesting a waiver of documentation of informed consent to conduct the consent process by phone. VA employee participants will be informed that audio-recorded interviews are involved and consent for audio-recording will be documented along with their consent to participate in the study. During the interviews, immediately after recording begins, study staff will ask all participants if they agree to being recorded. If not agreeable with recording, the recording will stop, but the interview will still proceed. This agreement/disagreement will be documented by study staff and stored in the study network drive where audio-recordings are stored. Other than their name, no other PHI will be collected from VA employee participants.

We will collect retrospective data, from the electronic medical records, for Veterans who receive BBTI from PCMH clinician at the participating sites. No information will be collected directly from Veterans; a waiver of informed consent and a waiver of HIPAA will be requested. Veterans will be receiving usual care (BBTI), thus, the risk to Veterans is minimal and limited to breach of confidentiality from the retrospectively collected data.

Study staff at the hub site and participating sites will complete and stay up to date on the required trainings for the conduct of human subjects research.

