|                    |            |                                                                                                                  |
|--------------------|------------|------------------------------------------------------------------------------------------------------------------|
| Diagnoses          | ICD-10:    | F51.0, F51.01, F51.02, F51.03, F51.04, F51.05, F51.09, G47.00, G47.01, G47.09                                    |
|                    | ICD-9:     | 307.41, 307.42, 780.50, 780.51, 780.52                                                                           |
| Sedative-hypnotics | On label:  | diphenhydramine, doxepin, eszopiclone, prazosin, ramelteon, suvorexant, temazepam, triazolam, zaleplon, zolpidem |
|                    | Off label: | hydroxyzine, melatonin, trazodone, others specifically indicated for sleep                                       |

Effectiveness will be measured as the change on the ISI from the initial score obtained (e.g., PCMH initial evaluation, BBTI/CBT-I session 1) to the last BBTI/CBT-I session. The ISI is commonly used within the VA and is easily accessible within VA electronic health records through the Mental Health Assistant toolbox as well as Behavioral Health Lab software, which was developed for use in PCMH. ISI data may also be extracted from CPRS progress notes (e.g., BBTI progress notes). The ISI has well-established psychometrics with good reliability and validity. It is standard practice as part of insomnia-related treatment (i.e., BBTI and CBT-I) and PCMH treatment (e.g., depression, anxiety, pain) to use measurement-based care (e.g., ISI, PHQ-9) and include outcome measures in progress notes to inform care and track treatment progress. For Effectiveness to be calculated, ISI scores from each BBTI/CBT-I session (e.g., entered in a BBTI progress note or CBT-I templated note) by PCMH clinicians will be extracted through the automated CDW queries to calculate outcomes for each Veteran. Rates of treatment response and remission will also be calculated. Response is a reduction of ≥8 points on the ISI from pre- to post-treatment. Remission is achieving a post-treatment response and an ISI <8. Previous BBTI trials found treatment response rates of 42-77% and remission rates of 28-53%.

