| Same day/PC patients (%) | 5.69                                                       | 5.46   | 5.35   | 5.24   | 5.13   | 5.02   | 4.80     |
| Power (%)                | 100                                                        | 100    | 99.96  | 99.02  | 90.03  | 59.25  | --       |

Descriptive statistics will be used to characterize the participating sites, PCMHI clinicians who are trained in BBTI (enrolled and not enrolled), and Veterans who received insomnia-related care in Primary Care/PCMHI (e.g., BBTI, CBT-I). Key enrolled clinician variables (self-report) will include socio-demographics, training, and work experience (e.g., degree, prior insomnia experience, duration working in PCMHI). For Veterans, variables of interest, from CPRS/CDW, include socio-demographics, vitals, service connection, combat history, and medical and psychiatric disorders, prescription medications, healthcare utilization, and information from progress notes (e.g., ISI scores). For Reach, Adoption, Implementation, and Maintenance outcomes, generalized linear mixed models will be used to compare the impact of the implementation strategy bundle across the three study phases for each site. These models will include a fixed main effect for study phase (pre, implementation, post) and random effects for clinician (nesting of Veterans within clinicians) and site (nesting of Veterans and clinicians within site); the primary comparison will be pre-implementation vs. implementation, with the secondary comparison implementation vs. post-implementation and long-term sustainability. Also, a we will conduct a comparison of outcomes from the study phases vs. a historical period prior to the study (1/1/20 – 12/31/20). While we did not power the study to assess interactions, to the extent possible, a fixed effect for site and the interaction between site and phase, will be introduced to assess differences between sites at the same study phase and differences between sites for the primary and secondary comparisons (e.g., differences from pre-implementation to implementation and from implementation to post-implementation, site 2 vs. site 3).

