For treatment Effectiveness, using an intent-to-treat approach, we will fit a linear mixed model that tests for BBTI effectiveness (reduction of ISI score over the course of treatment) that includes a main effect of time (evaluation to last treatment session) and includes random effects for Veteran (multiple measurements per Veteran during treatment), clinician (nesting of Veterans within clinicians) and site (nesting of Veterans and clinicians within site). We will also attempt to control for clinician experience on treatment outcomes as well as mode of delivery of BBTI (e.g., in-person, phone, video) and other adaptations, such as integrating other

therapeutic techniques as indicated per the progress notes and extracted as part of the data query process (e.g., behavioral activation, motivational interviewing). Rates of response and remission from treatment will be calculated as will treatment effect sizes.

Specific Aim 2: To identify specific strategies that help promote the implementation of BBTI in PCMH using qualitative interviews and utilization surveys.

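### The ISI time effect called a test of BBTI effectiveness is an uncontrolled pre-post change, and the model has no phase term to test the Aim 1 hypothesis for Effectiveness

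*Combined protocol and SAP*

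**What the plan says.** Section 5.6 (Data Analysis) states that for Effectiveness "we will fit a linear mixed model that tests for BBTI effectiveness (reduction of ISI score over the course of treatment", and that this model "includes a main effect of time (evaluation to last treatment session". The other named terms are random effects for Veteran, clinician and site, plus clinician experience, delivery mode and treatment adaptations, which the team will try to adjust for. Response and remission rates and effect sizes will also be calculated.

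Section 5.5 (Study Evaluations) defines the outcome as ISI change "from the initial score obtained (e.g., PCMH initial evaluation, BBTI/CBT-I session 1) to the last BBTI/CBT-I session", so CBT-I courses count along with BBTI courses. Section 5.3 (Informed Consent Procedures) describes the source: "We will collect retrospective data, from the electronic medical records, for Veterans who receive BBTI from PCMH clinician at the participating sites". Section 5.4 adds those who receive CBT-I.

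The aims are worded differently. Section 3.1 (Objectives) says "The hybrid design tests for level of" implementation and, in the same sentence, Veteran-level treatment effectiveness of BBTI. Aim 1 in that section is comparative: "We hypothesize that BBTI+IS will result in more Veterans obtaining insomnia-related care in PCMH (R [primary outcome]), better treatment outcomes (E". Yet section 5.6 reads "For Reach, Adoption, Implementation, and Maintenance outcomes, generalized linear mixed models will be used to compare the impact of the implementation strategy bundle" across the study phases, and Effectiveness is not in that list.

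**The concern.** Two questions are in play, and the planned test answers neither.

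The first is whether BBTI works as delivered in PCMHI. A main effect of time among treated Veterans has as its null that mean ISI does not change. That is not the null of no BBTI effect. Under the workflow in Table 2, the ISI is given at the visit where insomnia is confirmed as the key complaint and treatment is chosen, and that score may serve as baseline. Some fall on re-measurement is therefore plausible without any treatment effect.

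The second is whether BBTI+IS yields better treatment outcomes than training alone, which is the Aim 1 hypothesis for Effectiveness. A model without a phase term cannot address it.

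At stake is what the trial may say about Effectiveness. A significant time effect could be reported as evidence for BBTI when it shows only that scores fell, and the hypothesis actually stated could go untested.

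**Working it through.** The plan gives no power, sample size or detectable change for Effectiveness, so there is no figure of its own to reproduce here.

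**Step 1. What the time effect contains.** Expected change = BBTI effect (or CBT-I effect, since both are pooled) + natural course + regression to the mean. With no untreated ISI series, the parts cannot be separated.

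**Step 2. Rejection rate when the BBTI effect is zero.** Inputs:

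- n = 329 from section 5.2. This is a goal set for Reach; the number of Veterans with two ISI scores is not stated, so n = 82 is shown too.
- SD of change 5 to 7 points and natural fall d of 0.5, 1 or 2 points: assumptions. The documents give neither.
- Two-sided 5% level: assumption.

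The non-centrality is d / (SD/√n), and rejection follows from the noncentral t with n − 1 degrees of freedom. Example: n = 329, SD 6, d = 1. The standard error is 6/√329 = 0.331, the non-centrality is 1/0.331 = 3.02, and rejection is 85%.

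| Natural fall | n = 329, SD 5 / 6 / 7 | n = 82, SD 5 / 6 / 7 |
|---|---|---|
| 0.5 | 44% / 33% / 25% | 15% / 12% / 10% |
| 1 | 95% / 85% / 73% | 43% / 32% / 25% |
| 2 | over 99% for all | 95% / 85% / 72% |

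At n = 329 and SD 6, rejection reaches one half at a fall of about 1.96 × 0.331 = 0.65 points.

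**Step 3. Regression to the mean alone.** This was simulated with a stable true ISI and no recovery. Assumptions: population mean 14, true SD 4, error SD 2 to 3, entry on a first ISI of at least 11 or at least 15. Mean falls were 0.4 to 1.7 points. Rejection was 71-100% at n = 329 and 24-96% at n = 82. Without selection on the first score it was 4-6%. A mixed model with a Veteran intercept (n = 164, five visits, error SD 3, 60 runs) gave 3% with no selection, 65% with entry at 11 and 100% with entry at 15.

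**Step 4. What a phase contrast would do.** If the fall is the same in both phases, it cancels from the difference. A simulation with a 1.5-point fall in each phase, 164 Veterans per phase and SD (20.7 − 10.9)/2.3 = 4.26 (from the VA CBT-I study described in section 2.1) rejected in 4.0% of 4,000 runs. The detectable difference at 80% power, ignoring clustering, is (1.960 + 0.842) × SD × √(2/n per phase). The numbers per phase are illustrative, because the plan gives none:

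| Veterans per phase | SD 5 | SD 6 | SD 7 |
|---|---|---|---|
| 164 | 1.55 | 1.86 | 2.17 |
| 82 | 2.19 | 2.63 | 3.06 |
| 41 | 3.09 | 3.71 | 4.33 |

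Clustering and adjustment for calendar time would raise these. So would the design: under section 5.1, site 1 goes straight from training into implementation, so only three sites have a pre-implementation phase.

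**The case against.** The strongest reply has five parts.

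- **The label is defined where it is used.** Section 5.6 glosses effectiveness as a fall in ISI, as RE-AIM users often would, and nothing says it will be read causally. True, but section 3.1 presents the design as testing BBTI's effectiveness, so the caveat should be written down.
- **BBTI is treated as already established, and Reach is primary.** This stands. It supports reporting pre-post change descriptively, not calling it a test, and it limits the weight of the point.
- **The plan is not confined to a comparison with zero.** Response, remission and effect sizes are planned, earlier trial rates are cited, and fidelity is measured separately. This stands. What is missing is intervals and a stated way to read the results.
- **Comparisons exist elsewhere.** Under Maintenance, section 5.5 compares the sustainability periods with earlier phases, and section 5.6 adds a comparison with 2020. So a reader should not infer that Effectiveness is never compared with anything. Neither comparison sets BBTI against no BBTI, and neither is written as an ISI-change contrast of pre-implementation with implementation.
- **The natural fall may be small.** Section 3.1 says that untreated insomnia stays chronic, section 5.1 puts treatment at four to five weeks, and section 5.4 sets no ISI entry cut-off. This stands as a limit on size. A reader might infer that rejection is close to certain even if BBTI does nothing. The documents do not support that: it needs a fall of roughly 1 to 2 points at n = 329.

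**Conclusion.** The point holds in this form. The time effect measures uncontrolled pre-post change, pooled over BBTI and CBT-I, and cannot serve as a test of BBTI's effectiveness. That conclusion is logical and needs no assumed figures. The size does: with zero BBTI effect, rejection at n = 329 runs from about 25% to over 99% as the assumed natural fall goes from 0.5 to 2 points (SD of change 5 to 7). At n = 82 the range is about 10% to 95%.

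The missing phase term matters as much, because the only stated hypothesis for Effectiveness is the comparison of BBTI+IS with training alone. It would be wrong to say that the trial's stated hypothesis is that BBTI works; Aim 1 does not say so. The point concerns a non-primary outcome and leaves the primary Reach analysis untouched.

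**What to change.** In section 5.6:

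1. Describe the model as one that *estimates within-Veteran ISI change during treatment*, and state that a significant time effect will not be read as evidence of a BBTI effect.
2. Report mean change, response and remission with 95% intervals, and read them against the rates already cited in section 5.5 (response 42-77%, remission 28-53%). Note that those rates come from treated patients and also contain natural change. They can reveal weak delivery, but they do not isolate BBTI.
3. Add study phase and time-by-phase terms, with calendar time, as the test of the Aim 1 hypothesis for Effectiveness. State that its power is not established. This contrast compares phases among treated Veterans, so it still says nothing about BBTI against no treatment.

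Change from evaluation to session 1 may be shown descriptively where both scores exist. It should not be offered as untreated change: Table 2 has the evaluation visit starting a change plan, and section 5.5 lists the two scores as alternative baselines.

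The cost is wording and a few model terms on data already being extracted. The price is a weaker headline for Effectiveness and an imprecise phase contrast.

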## 5.7 Withdrawal of Subjects

Participation by VA staff (site PIs and PCMH clinicians) is voluntary. After informed consent is completed and the VA staff participants are enrolled, they can withdraw at any time. To do so, the participant will inform their site's research assistant and/or PI, who will then inform the study PI; alternatively, the participant can inform the study coordinator and/or study PI.

An anticipated circumstance for withdrawal of a PCMH clinician would be if the participant changed positions and no longer delivered care in PCMH and/or stopped working at the participating VAMC. If this were to occur, similar procedures as above can be followed to inform study leadership.

There are not follow-up phases to participate in if a participant withdraws. As a minimal risk study, there are not anticipated safety concerns that would require follow-up after withdrawal.

## 6.1 Reporting

This is a minimal risk study. Any unanticipated problems, serious adverse events, and/or deviations will be reported according to the "Table of Reporting Requirements to the VA Central IRB." Any reportable events that occur at the participating sites will be reported by the site PI to the study PI, who will then submit the

information to the Central IRB. Reportable events that occur at the hub site will be reported to the Central IRB by the study PI immediately.

There is no Data Monitoring Committee for this study.

## 7.1 Privacy and Confidentiality

This study will collect PHI but will not disclose PHI. All data collected and obtained during the study will be confidential. Data collection and management will be conducted in strict accordance with the policies and procedures set forth by the VA Office of Research and Development.

### *Data Management*

[name] (PI) will oversee all aspects of the study and data management. The VAPHS Center for Health Equity Research and Promotion (CHERP) Biostatistics and Informatics Core (BIC) will provide data management and statistical support. The PI and study team will standardize all staff training and procedures. Any databases and necessary data entry forms will be developed by BIC personnel and/or study staff and stored on a VA server maintained by OI&T in a study-specific network drive with access limited to the research team. All participants, site PIs and PCMHI clinicians, will be identified with unique study IDs that do not include PHI. Unique study IDs will also be used for the retrospective data collected for Veterans from the electronic health records. The PI, project coordinator, data manger, and other relevant study staff will ensure that study protocols and procedures are followed, that data integrity and confidentiality are maintained, and that incorrect and missing data are minimized.

### *Data Security*

All data, for site PIs and PCMHI clinicians (from qualitative interviews and surveys) and for the retrospective data collected for Veterans (from VA CDW), will be identified with unique study IDs. Any hard copy study documents will be kept in a locked file cabinet within locked offices of the study staff (VAPHS, [name]). The study data managers/programmer analysts will be responsible for removing PHI prior to any data review or analysis by members of the study team. Electronic data will be stored on a secure study network drive with limited access to the study team. Coded interview data will be manually entered by study staff into a database that will be stored on a secure study network drive located behind the VA secure firewall.

Windows integrated security will be used for all computer access. At the VA, all PCs, laptops, workstations and remote devices are set to lock and are secured after being left unattended for 5 minutes or more, or by logging-off when the equipment will be unattended for an extended period. User and role permissions will be defined at the computer-, directory-, and server-level. Source documents with private information (e.g., consent document, payment form, etc.) will be stored in a locked file cabinet within the locked office of study staff. Research records may be released or disclosed if required by federal law. Participants will not be specifically identified in any publication of research results. Records will be stored and maintained per current VA regulations.

